C.6.e.4. Assessment of the proportion of children who are up-to-date (UTD) on immunizations at each practice: We will conduct a retrospective analysis of UTD status for all recommended childhood vaccines among children 19-35 months old at each practice using vaccine administration data for each practice obtained from the two state's immunization registries (WAIIS and CIIS). The WAIIS and CIIS operate in accordance with nationally recommended standards for immunization registries, and all PSPRN and COCONet practices participate in CIIS or WAIIS. Both CIIS and WAIIS use birth certificate data to identify children and cover ≥95% of children <6 years old in their respective states.¹¹¹ Both CIIS and WAIIS¹¹² combine the immunization information from multiple sources into a consolidated, complete, and valid record of immunizations. Data quality assessments are done frequently. Offices are required to have <5% error rate in the registry, making these registries a highly accurate data source for assessing vaccine utilization.

C.6.f. Intervention: Intervention specifics will ultimately be determined through the iterative process detailed in Aim 1 (see *C.5.c.-d.*). Therefore, what follows is preliminary and will be modified. At baseline, providers at intervention practices will be electronically sent a link to the online video module to view at their convenience. Modules will be approximately 30 minutes and will be encoded with a viewing tracker that will enable study staff to monitor its completion. Providers who have not viewed the module within 2 weeks will be sent up to 3 reminders with additional links to the video module. The window for viewing the video module will be 30 days, and viewing the video will be required for provider to receive MOC Part 4 credit. Based on our previous study utilizing a baseline video module (see *C.1.d.*), we expect a $\geq 70\%$ completion rate.

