C.6.h. Blinding: Given our intervention, it is not possible to blind providers or investigators to study-arm allocation. However, our analysts will be blinded to study-arm allocation. We will also minimize selection bias by including all parents whose newborns receive health supervision at participating practices in the study and analysis. We will minimize participant bias by blinding providers to PACV-SF scores of parents and parent ascertainment bias by masking the PACV-SF during enrollment by embedding it in a larger survey.

C.6.i. Primary Study Outcome: Our primary outcome will be the immunization status of children of VHPs at 19 months, 0 days of age expressed as the mean percentage of days under-immunized from birth to 19 months for 22 doses of 8 vaccines recommended during this interval (3 Hepatitis B, 3 Rotavirus, 4 Diphtheria, tetanus, and acellular pertussis [DTaP], 3 *Haemophilus influenzae*, type b [Hib], 4 Pneumococcal conjugate, 3 Inactivated poliovirus [IPV], 1 Measles, mumps, rubella [MMR], and 1 Varicella). To calculate the mean percentage of days under-immunized, we will sum the days late for each dose and divide this by the maximum number of days a child could be late if they had received none of the total 22 doses for the 8 vaccines by 19 months. We have chosen to use the mean percentage of days under-immunized because it is a sensitive measure of under-immunization by accounting for missed vaccines doses and delay in receipt of vaccines.¹¹⁷ We have successfully used this measure in previous studies (see C.1.a. and C.1.c.). We will obtain immunization data from WAIIS and CIIS as described in C.6.e.4. As an exploratory secondary outcome, we will also measure the immunization status of children of non-VHPs (expressed as the mean percentage of days under-immunized) since the PIVOT with MI intervention involves use of the presumptive format with all patients and therefore has the potential to also impact the vaccine behavior of non-VHPs.

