C.6.j. Analysis: We will conduct an intention-to-treat analysis. The patient will be the unit of analysis. We will examine baseline characteristics of parents in control and intervention arms using Pearson's χ^2 tests (or Fisher's exact tests) for categorical variables and t-tests for continuous variables to assess for any unbalanced confounders. Any unbalanced confounders will be controlled for as covariates in all subsequent regression analyses. We will also compare baseline characteristics between parents with and without missing data. We will apply sensitivity analysis and multiple imputations techniques to address missing data.

Given the nested structure of the data, we will apply mixed effects regression models to examine the effects of the intervention on our primary outcome while controlling for covariates and accounting for correlations due to clustering. Let y_{ijk} denote the percent days under-immunized for child k who receives care from provider j at clinic i , let T_{ijk} be the intervention indicator (0=control, 1=intervention) for the child, let X_{ijk} be the collection of covariates that includes potential confounders (at patient, provider, or practice levels), then a mixed model that accounts for this specific nesting data structure can be specified by

$$y_{ijk} = T_{ijk}\alpha + X_{ijk}\beta + Z_{ijk}^{(3)} u_i^{(3)} + Z_{ijk}^{(2)} u_{ij}^{(2)} + \epsilon_{ijk}, \quad (1)$$

for $k = 1, \dots, n_{ij}$ first-level observations (patient) nested within $j = 1, \dots, M_i$ second level groups (provider), which are nested within $i = 1, \dots, M$ third-level groups (practices). $Z_{ijk}^{(3)}$ and $Z_{ijk}^{(2)}$ are design matrices for the third- and second-level random effects. Further normality and independence assumptions will be placed on random effects and error terms if the outcome is continuous. The above model specification represents a multi-level linear mixed model. Parameter estimates will be obtained through restricted maximum likelihood estimation. Robust sandwich standard error estimates to account for the clustering will be used for inference. In the above model specification, the parameter α captures the expected difference between intervention and control arms and will be our focus of inference. For binary outcomes, the above model specification can be adapted to mixed effects logistic regression with similar estimation and inference techniques.¹¹⁸

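### A child with some recorded doses who then leaves the state is scored as late to 19 months for every later dose, and nothing in the plan treats that score as missing

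*Combined protocol and SAP*

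**What the plan says.** Section C.6.i. of the combined protocol and SAP defines the primary outcome, at 19 months 0 days, as the days late added up over 22 doses of 8 vaccines. The analyst is then to "divide this by the maximum number of days a child could be late if they had received none of the total 22 doses". The measure is preferred because it is sensitive, "accounting for missed vaccines doses and delay in receipt of vaccines". The source is also fixed there: "We will obtain immunization data from WAIIS and CIIS as described in C.6.e.4".

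Section C.6.e.4. describes the registries. They "cover ≥95% of children <6 years old in their respective states", they "combine the immunization information from multiple sources into a consolidated, complete, and valid record of immunizations", and "Offices are required to have <5% error rate in the registry".

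Section C.6.h. keeps all parents of newborns at participating practices in the analysis, and C.6.j. specifies intention to treat. On missing data, C.6.j. says "We will apply sensitivity analysis and multiple imputations techniques to address missing data" and "We will also compare baseline characteristics between parents with and without missing data". It does not say what makes the primary outcome missing. No section covers moves out of state, failure to match a registry record, or a last date of observation.

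**The concern.** The score cannot tell a dose that was not given from a dose given where the registry does not see it. Suppose a child has registry doses at 2 and 4 months and then moves to another state. The formula still returns a number. The denominator still covers all 22 doses to 19 months, and each later dose counts as missed. Since a number is present, this child does not appear in the comparison of parents with and without missing data and is not passed to imputation.

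Three things are at stake. False lateness raises the arm means and the SD. The arm difference shrinks, because part of each leaver's score no longer reflects vaccination behaviour. If leaving differs by arm, the contrast is biased: more leaving in the intervention arm makes the intervention look worse, and more in the control arm makes it look better. The sample-size section (C.6.k.) varies hesitancy prevalence and SD, but makes no allowance for loss.

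**Working it through.** **Inputs from C.6.k.:** mean 26.2%, said to equal 37 days late per dose; target decrease 10 days; SD 20; ICC 0.02; alpha 0.05; 300 per arm; 24 practices of 25. The unit of the SD is not stated and is read as percentage points. Alpha is taken as two-sided.

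**The plan's own figure.**
- Effect = 26.2 × 10/37 = 7.08 points.
- Design effect = 1 + 24 × 0.02 = 1.48, so effective n = 300/1.48 = 202.7 per arm.
- Standard error = 20 × √(2/202.7) = 1.99, and 7.08/1.99 = 3.56.
- Power = 94.6% (normal) or 92.6% (t, 22 df). The claim of at least 90% is reproduced.

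**False gain per leaver.** Assume departure age *a* is uniform on 1–19 months, and that leavers would otherwise have been late for 26.2% of the remaining days, like other hesitant families. The false gain is then (100 − 26.2) = 73.8 points times the share of the maximum days that belongs to doses due after *a*.

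*Due dates spread evenly over 0–19 months.* Share = ((19 − a)/19)². Its mean is 18²/(3 × 19²) = 0.299 and its mean square is 18⁴/(5 × 19⁴) = 0.161. Mean gain = 73.8 × 0.299 = 22.1 points. Mean squared gain = 73.8² × 0.161 = 877.

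*Front-loaded due dates.* The due ages are an illustrative assumption, not taken from the plan: 1 dose at birth, 1 at 1 month, 5 each at 2, 4 and 6 months, 4 at 12 and 1 at 15.
- Maximum dose-months = 19 + 18 + 85 + 75 + 65 + 28 + 4 = 294.
- A dose due at age d falls after departure with probability (d − 1)/18. The mean lost is (85×1 + 75×3 + 65×5 + 28×11 + 4×14)/18 = 999/18 = 55.5.
- Mean share = 55.5/294 = 0.189, so mean gain = 13.9 points. Mean squared gain = 527.

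**Effect on the trial**, with the same leaving proportion p in both arms:
- rise in arm mean = p × gain
- SD = √(400 + p × mean squared gain − (p × gain)²)
- effect = 7.08 × (1 − p × mean share)

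| Due dates | p | Rise in mean | SD | Effect | Power (t, 22 df) |
|---|---|---|---|---|---|
| Front-loaded | 5% | 0.7 | 20.6 | 7.01 | 90% |
| Front-loaded | 10% | 1.4 | 21.2 | 6.95 | 88% |
| Even | 5% | 1.1 | 21.0 | 6.98 | 89% |
| Even | 10% | 2.2 | 22.0 | 6.87 | 85% |

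Dropping the same children as missing, with SD 20 and effect 7.08, gives 92% at 5% and 91% at 10%.

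**Unequal leaving.** A 3-point arm difference shifts the contrast by 0.03 × 13.9 = 0.42 to 0.03 × 22.1 = 0.66 points, which is 6–9% of 7.08. With equal leaving the shift under the null is zero.

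**The case against.** The strongest reply is that the scoring of absent records is inferred. The formula speaks of doses received, not doses recorded, and no sentence says that an absent record means an unvaccinated child. For a child with no registry match, this reply succeeds. A reader might infer that such children are scored as wholly unvaccinated and that imputation never reaches them, but the documents do not say so. With no dose dates there may be no score at all, and C.6.j. could treat the outcome as missing. The large losses that full scoring would cause (5% of children at 100% gives SD 25.8 and power of about 71%) therefore cannot be charged to the plan as written.

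For the child with a partial record, the reply fails. The registries are the only named source, so a dose given elsewhere looks like one never given unless it is reported back, and the formula yields a number regardless.

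Second, C.6.e.4. describes consolidated and checked registries. This stands for moves between practices within a state, which need not lose doses. It does not cover children who have left. Nor does the coverage figure measure moves, so it should not be read as a 5% leaving rate.

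Third, C.6.k. already considers SD 25, above anything in the table. That scenario requires approaching 12,000 parents (1,200 pairs at 10% prevalence). The enrolment target remains 600 pairs, and a larger sample would not remove bias from unequal leaving.

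Fourth, the size is modest and rests on an assumed leaving rate. That stands.

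**Conclusion.** The point holds for children with some registry doses who then leave the state: under C.6.i. they receive a falsely high score, and C.6.j. gives no ground for treating it as missing. For children with no match the plan is silent, and the request is only that it state a rule.

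The damage is moderate. At an assumed 5% leaving, power is about 90–89%, at the edge of the plan's own 90% target. At 10% it is 88–85%, below the target. Bias arises only if leaving differs by arm, and a 3-point difference gives 0.4–0.7 points. These figures rest on assumed leaving rates, uniform departure ages, two assumed patterns of due dates, SD 20 in percentage points and an unchanged ICC of 0.02. A reader might infer a raised false-positive rate in general; with equal leaving there is none, only dilution and lost power.

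**What to change.** Before registry data are scored, add to C.6.i. and C.6.j.:

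1. A child with no registry match has a missing primary outcome.
2. For a child recorded as having left the state, doses due after the departure date are unobserved. The 19-month score comes from the planned multiple imputation, with the record up to departure as a predictor. A score truncated at departure should not also serve as the primary value, because it covers a different interval from the defined outcome.
3. Departures are identified from the same source and by the same procedure in both arms, blind to arm where possible. Study champions exist only in intervention practices, so they should not be the route.
4. Unmatched and departed counts are reported by arm.
5. The as-written scoring is kept as a pre-specified sensitivity analysis.

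The cost is SAP wording, a departure flag and one extra analysis, with no change to design, enrolment or intervention. There are two small downsides: recorded departures may be incomplete, and imputation assumes that later doses can be predicted from the observed record.

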C.6.e. Covariate-constrained Randomization: Practices will be the unit of randomization. A key issue in cluster-randomized trials is the possibility of covariate imbalance in practices assigned to different treatment arms.¹⁰⁴⁻¹⁰⁸ Thus, practices will be randomly assigned to assure balanced comparison groups using optimized probability sampling to the intervention or control arm in the following manner. From the pool of practices that agree to participate in the study, pre-study information will be collected on several characteristics that may influence study outcomes: percent of VHPs, percent of Vaccines-for-Children [VFC]-eligible patients, number of pediatric providers, and practice immunization rates of children 19-35 months old. These pre-study variables will then be used to develop and evaluate a balance criterion, defined as the sum of the squared differences between standardized practice means on these variables.¹⁰⁵ All possible combinations of eligible practices in 2 arms (intervention and control) will be generated using a SAS macro program.¹⁰⁷ The distribution of the balance criterion for the 2 study arms will be used to define an acceptable set of study arms that are reasonably balanced in terms of the selected variables (minimum 10% of balance criterion).¹⁰⁵ From this set, one set will be chosen at random and used to randomly assign each practice to intervention or control arms. This process will be undertaken in both Colorado and Washington as separate randomization procedures. We have successfully used covariate-constrained randomization in C.1.d. and other studies.^{109,110}

We will perform the following procedures to obtain pre-study information on these covariates:

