C.6.g. Data Collection and Implementation: During the intervention period, all English- and Spanish-speaking parents of newborns will be screened with the PACV-SF prior to their initial visit at a participating practice by integrating the PACV-SF into standard practice workflow (see *C.6.e.1.*). The PACV-SF will also include demographic items that have been associated with under-immunization (birth order of their child, household income, marital status, parent self-designated race/ethnicity, gender, and number of children in their household)^{31,113-115} and be embedded in a larger survey to minimize ascertainment bias.

To assess intervention fidelity (Aim 2a), a study RA will approach by phone English-speaking VHPs attending intervention practices who answer affirmatively to an item on the PACV-SF asking for their permission to contact them to determine their interest in participating in a study of provider-parent communication at health supervision visits in which their child’s visit will be videotaped. We will describe the study generally to parents in order to minimize the chance that parents alter their behavior to meet observer expectations. We will approach VHPs continuously throughout the intervention period to obtain a collection of videotaped encounters at different time periods to assess whether there is a waning of fidelity over time. We have chosen videotaping because it captures aspects of nonverbal communication that are (a) not captured by audiotaping alone and are essential to our study of vaccine acceptance (e.g. head nodding) and (b) necessary to provide visual feedback to providers during the 12 month refresher session (see *C.6.f.*).¹¹⁶ For those VHPs who are interested (based on our past studies, we expect $>70\%$ will be interested [see *C.1.c.*]), the study RA will meet the parent at their child’s next health supervision visit to obtain their written informed consent. The child’s visit will then be videotaped using a video-recorder equipped with a wide-angle lens and positioned in a corner of the exam room near the ceiling, consistent with the methods we have used in preliminary studies (see *C.1.c.*). All videotaped visits will be transcribed. Parents will receive a \$25 gift card for participating.

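### C.6.j fixes the structure of the primary model but leaves its covariate set and its small-sample inference on 24 practices open

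*Combined protocol and SAP*

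**What the plan says.** Section C.6.e randomizes practices within a constrained set. The balancing variables are "percent of VHPs, percent of Vaccines-for-Children [VFC]-eligible patients, number of pediatric providers, and practice immunization rates of children 19-35 months old", described as "several characteristics that may influence study outcomes". On state it adds: "This process will be undertaken in both Colorado and Washington as separate randomization procedures".

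Section C.6.j sets out the primary analysis: intention to treat, with patients nested in providers nested in practices, a linear mixed model fitted by REML, and the arm coefficient as the quantity of interest. The covariate term is "the collection of covariates that includes potential confounders (at patient, provider, or practice levels"), with no variable named.

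The only stated selection rule concerns parents. "We will examine baseline characteristics of parents in control and intervention arms", it says, by chi-square, Fisher or t-tests, and then: "Any unbalanced confounders will be controlled for as covariates in all subsequent regression analyses". No threshold for imbalance is given, and the tests named ignore clustering.

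On inference: "Robust sandwich standard error estimates to account for the clustering will be used for inference". No small-sample correction, reference distribution or degrees of freedom is given.

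Section C.6.g says the screening survey will also collect "demographic items that have been associated with under-immunization". There are six: birth order, household income, marital status, race/ethnicity, gender and number of children at home. None is named for the model. Section C.6.h says the analysts will be blinded to arm.

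**The concern.** There are three gaps, and they interact.

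1. Five variables shape the allocation (state and the four practice variables), but the analysis is not tied to any of them. The covariate term permits practice-level variables, so a model with all five and a model with none both fit the text.
2. Parent covariates enter according to observed imbalance. Chance in the enrolled sample then decides the adjustment set, although the plan already lists items it regards as related to the outcome.
3. With 24 practices, an uncorrected sandwich tends to be too small, and more so as practice-level covariates are added. A careful analyst who adjusts for the randomization variables would therefore worsen the false-positive rate unless a correction comes with the adjustment.

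At stake are the nominal 5% error rate (gaps 1 and 3) and a primary covariate set that is known in advance (gaps 1 and 2).

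**Working it through.** **Inputs from C.6.k:** 24 practices with 25 pairs each, 300 per arm, SD 20, ICC 0.02, alpha 0.05 (taken as two-sided), and a 10-day reduction from 37 days, where 37 days corresponds to 26.2%.

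**Assumed, because the documents give no figure:** 12 practices per state, split 6:6; practice sizes either equal or with a coefficient of variation (CV) of 0.5; and f, the share of between-practice variance explained by state and the four covariates, set at 0, 0.5 and 0.8. The sandwich is taken as clustered on practice.

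**Step 1. The plan's power.** The effect is 26.2 × 10/37 = 7.08 points, reading SD 20 in percentage points. The design effect is 1 + 24 × 0.02 = 1.48. The standard error is 20 × √(1.48 × 2/300) = 1.99, so the noncentrality is 7.08/1.99 = 3.56. Power is 94.6% (normal), 92.6% (t, 22 df) or 91.9% (t, 17 df). The stated 90% or more is reproduced.

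**Step 2. Arm only, uncorrected sandwich, closed form.** With 12 equal practices per arm the uncorrected variance is too small by 11/12. Under simple randomization, type I error against a normal reference is P(|t22| > 1.96 × √(11/12)) = 7.4%. With the t22 critical value (2.07) it is 6.0%.

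**Step 3. The same test under the planned randomization.** Simulation with 40,000 runs per cell, allocation drawn from the best 10% of the 924 splits in each state, ICC 0.02. Type I error (%) for the arm-only model:

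| Practice sizes | Reference | f=0 | f=0.5 | f=0.8 |
|---|---|---|---|---|
| Equal | normal | 7.4 | 5.5 | 4.4 |
| Equal | t, 22 df | 6.0 | 4.3 | 3.4 |
| CV 0.5 | normal | 8.2 | 5.9 | 5.0 |
| CV 0.5 | t, 22 df | 6.7 | 4.7 | 3.9 |

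The error can go either way. At ICC 0.05 with equal sizes, the normal-reference figures are 7.4, 4.1 and 2.4%.

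**Step 4. Design variables added.** Practice-level degrees of freedom are 24 − 7 = 17 (intercept, arm, state and four covariates). At ICC 0.02, across all f:
- Uncorrected, normal reference: 11.8–12.0% (equal sizes), 12.7–13.2% (CV 0.5).
- Uncorrected, t on 17 df: 9.4–9.7% and 10.2–10.6%.
- Mancl-DeRouen correction, t on 17 df: 2.3–2.4%.
- Kauermann-Carroll correction, t on 17 df: 5.0–5.6% in all 16 cells run (ICC 0.02 and 0.05, with and without parent covariates).

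With the correction applied to both, the arm-only and design-adjusted models still give different verdicts at 5% in 2.6–3.9% of null trials. That part comes from covariate choice and not from the uncorrected sandwich.

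**Step 5. The baseline screen.** For a covariate with no true difference, tested unclustered at an assumed p<0.05, the flag rate is 2 × (1 − Φ(1.96/√(1 + 24 × ICC))). At covariate ICCs of 0, 0.02, 0.05 and 0.10 (assumed) this is 5, 11, 19 and 29%. The chance that at least one of six is flagged, if they are independent, is 1 − (1 − q)^6, where q is the flag rate: 26, 49, 71 and 87%.

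A patient-level simulation looked at the effect on type I error (8,000 runs per cell; five providers per practice, provider ICC 0.01, CV 0.5, six parent covariates with ICC 0.05 jointly explaining 10% of variance, all assumed). The arm-only uncorrected normal test gave 8.2, 6.6 and 5.1% without the screen and 7.2, 5.8 and 4.4% with it, at f = 0, 0.5 and 0.8. The screen does not inflate the error.

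**Step 6. Power (%), corrected sandwich in both models, ICC 0.02.**

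| Practice sizes | Model | f=0 | f=0.5 | f=0.8 |
|---|---|---|---|---|
| Equal | Arm only, 22 df | 92.6 | 93.7 | 94.8 |
| Equal | Design-adjusted, 17 df | 90.6 | 94.9 | 97.0 |
| CV 0.5 | Arm only, 22 df | 91.2 | 92.0 | 93.1 |
| CV 0.5 | Design-adjusted, 17 df | 88.2 | 92.9 | 95.7 |

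**The case against.** C.6.j already settles a good deal: outcome, intention to treat, nesting, estimator and target parameter. Blinded analysts cannot easily choose covariates to favour an arm. Silence about a correction is not a decision to omit one, and some software applies one, or a t reference, by default. The 11–13% figure needs three things together that the plan allows but does not state: all five design variables, no correction, and a normal reference. The arm-only reading is close to nominal, and its highest values need design variables with no influence, although C.6.e chose them because they might have some. The at-least-one-of-six rates assume independence, yet birth order and number of children are plainly related, so those rates are too high.

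All of this stands as a limit on the point. It does not remove it. Blinding restrains favourable choice without fixing the model. Relying on software defaults leaves the error rate to the package: a t reference on 17 df alone still gives 9–11%, and Mancl-DeRouen gives about 2%.

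A reader might infer that the whole primary model is undefined, that the planned test has a false-positive rate above 10%, or that baseline screening inflates that rate. The documents do not support these readings. The structure is fixed, the high rate belongs to one permitted combination, and the screen slightly lowered the error where it was simulated.

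**Conclusion.** The point holds for the covariate set and the reference distribution only. On the plan's SD and ICC, the permitted analyses have type I error from about 3–8% (arm only, uncorrected) to about 9–13% (design variables added, uncorrected), and the text does not say which applies. The lower range depends on the assumed f. The upper range hardly moves with f and rises by about one point with unequal practice sizes. The harm from the baseline screen is that chance imbalance selects the adjustment set; no added type I error was found. The sample size is not undermined, since the stated power is reproduced. This should be changed, but it does not invalidate the design.

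**What to change.** In C.6.j, name the primary model in full: arm, state, the four constraint covariates in the form used in the balance criterion, and all six parent items listed in C.6.g with their coding, whatever balance is observed. Keep baseline comparisons as description only. In the same edit, name the inference: a Kauermann-Carroll (CR2-type) corrected sandwich clustered on practice, with t on 17 df.

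The covariates and the correction must change together, because added covariates make the uncorrected sandwich more liberal. The particular correction must be named: Mancl-DeRouen on 17 df costs 4–11 points of power at ICC 0.02. Kenward-Roger should not be listed as an equivalent unless it is checked first. Only a model-based stand-in on 17 df was run (3.4–5.2% type I error), and Kenward-Roger estimates its own degrees of freedom, which need not be near 17 when the practice variance is estimated at zero.

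The cost is wording plus five practice-level degrees of freedom (critical value 2.07 to 2.11); every variable is already to be collected. If the practice covariates explain nothing, power falls from 92.6% to 90.6% with equal sizes, and from 91.2% to 88.2% with CV 0.5, which is below the stated 90%. It rises if they explain half or more of the practice variance. Parent covariates jointly explaining an assumed 10% of variance offset the loss in the patient-level simulation at f=0 (87.8% arm-only, 88.8% with the full model), but that is still under 90%.
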